## STUDY PROCEDURES

### 1. CONSENT FORM 2. STUDY QUESTIONNAIRES

- Leicester-cough questionnaire (LCQ) at baseline, 6 weeks, 12 weeks
- Cough VAS scale at baseline, 6 weeks and at 12 weeks
- GERD-QoL questionnaire (GERD-QoL) at baseline and at 6 weeks
- Sino-nasal outcome test (SNOT-20) at baseline and at 6 weeks
- Asthma life questionnaire at baseline and at 6 weeks
- Laryngeal dysfunction scores (LDQ) at baseline and at 6 weeks

3. Cough monitoring for 24 hours, at baseline and at 6 weeks and 12 weeks.
4. CPAP data download at 6 weeks, 12 weeks
5. Exhaled breath condensate at baseline, 6 weeks and 12 weeks.

Once patients are enrolled, they will be randomized to either straight CPAP or sham CPAP. Randomization will be done by study coordinator, [name] and treating physicians (and investigators) will be blinded to whether the patient received straight CPAP or sham CPAP. Patients will be evaluated at 6 and 12 weeks after randomization as part of study. At 6 weeks, patients will be unblinded and placed back on straight CPAP. The pressure on straight CPAP will be determined according to the results of the polysomnography or they will be kept on 10cm of CPAP (adjustments to this may be made by the study coordinator, [name] who is the CPAP coordinator for the Sleep Center). For sham CPAP, patients will be kept at 1-2cm of pressure as per sham CPAP recommendations and no adjustments to this will be made although there may be adjustments made in mask or interface used for the CPAP.

---

## Statistical Methods, Data Analysis and Interpretation

---

### PRIMARY END-POINT

1. Change in LCQ score in CPAP-treated patients vs. sham CPAP-treated patients. This will be compared between baseline LCQ score prior to initiation of CPAP or sham CPAP and compared to the LCQ score at 6 weeks.
2. Change in Leicester cough monitoring measured at baseline and at 6 weeks after CPAP or sham-CPAP therapy.
3. Change in measurements of exhaled breath condensate 8 isoprostane, IL-6, nitrite/nitrate, H2O2 and LTB4 at baseline and at 6 weeks.

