## **Background and Introduction**

---

Chronic cough patients are treated for the etiologies of gastroesophageal reflux disease (GERD), cough variant asthma (CVA), upper airway cough syndrome (UACS) formerly called postnasal drip syndrome with varying benefit (4). Despite prolonged therapies with agents directed at GERD, UACS and CVA, these patients continue to experience persisting cough that is termed as idiopathic cough or unexplained cough. Studies have shown that cough can be unexplained or idiopathic in up to 42% of patients (5).

Obstructive sleep apnea (OSA) is a highly prevalent condition in the general population (6). A large retrospective study performed at Utah Valley Pulmonary Clinic identified a 44% prevalence of OSA in chronic cough population. 93% of patients treated with CPAP showed improvement in cough (2). Besides this study, a number of case reports have identified OSA as a perpetuating cause for chronic cough (7-8). Based on this, a number of mechanistic pathways by which OSA can lead to or perpetuate chronic cough have been identified (3).

Despite above reports, no study has conclusively shown that CPAP therapy alone provides improvement in cough relief as patients with chronic cough are often rendered multiple different therapies for GERD, CVA and UACS. Additionally no study till date has used a placebo arm to demonstrate improvement in cough intensity measurements with CPAP therapy.

The current study purports aims to establish a definitive relationship using a CPAP vs. sham CPAP arm to assess changes in subjective and objective cough measures in chronic cough patients with comorbid OSA. Sham CPAP therapy is a well-established modality to demonstrate efficacy of OSA therapy on a multitude of disease states, ranging from metabolic syndrome to reflux disease (9).

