## **Purpose and Objectives**

---

**AIM:** To demonstrate that therapy of concomitant OSA in patients with chronic cough improves or resolves chronic cough.

Chronic cough is an important clinical problem in primary care and subspecialty practice (1). Besides the distress experienced by patients with chronic cough, significant healthcare resources are expended to understand the role of gastroesophageal reflux, asthma and post-nasal drip in understanding their contribution to cough.

Recently obstructive sleep apnea (OSA) has been found to be common in patients with chronic cough (2). More importantly, treatment of OSA with continuous positive airway pressure (CPAP) led to improvement in cough in chronic cough patients (2). Mechanisms by which

OSA therapy with CPAP can improve cough includes beneficial effects on reflux and airway inflammation (3).

Our study purports to definitively establish that CPAP therapy for treatment of OSA in chronic cough patients improves cough. While these patients with chronic cough are not routinely screened and treated for OSA, our study aims to evaluate these chronic cough patients with screening questionnaires for OSA and if necessary with polysomnography and randomize them to either CPAP or sham CPAP for 6 weeks. During this 6 weeks patients will undergo assessments for cough using the following

- Validated cough questionnaires
- Objective cough monitoring using cough monitors provided by [name] in UK
- Measures of airway inflammation using exhaled breath condensate.

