## PATIENTS ON STRAIGHT CPAP FOR 6 WEEKS

## VISIT 3 (+12 wk) ADMINISTRATION OF LCQ, SMART-CARD DATA DOWNLOAD, EBC

## STATISTICAL ANALYSES

Each patient will serve as his or her control in terms of 6 weeks assessment of LCQ change following sham CPAP or straight CPAP therapy. Similar analyses are expected for GERD-QoL scores, Cough monitoring and EBC assessments.

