## NUMBER OF SUBJECTS TO BE ENROLLED

Based on the results of a recently concluded CPAP intervention study for chronic cough, mean change in LCQ with CPAP was + 4.1 (with 4.14 SD in baseline and followup LCQ scores)

Mean change in LCO with placebo was 1.1 (Lancet 2012)

Expected difference between mean LCOs of two groups 3.0

- To achieve 80% difference to detect a significant difference of 0.05 level for a difference means of 2.58, 19 subjects per group needed assuming no attrition using a mixed models analysis of repeated measures data.

- Assuming 33% attrition rate due to CPAP noncompliance, 29 subjects per group needed.

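### Seven measurements are listed as primary with no lead end-point, testing order, success rule or multiplicity adjustment; the 0.05 level and sample size are given only for LCQ

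*Combined protocol and SAP*

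**What the plan says.** The section headed "PRIMARY END-POINT", in the singular, has three numbered items. The first is the questionnaire, compared between the arms: "Change in LCQ score in CPAP-treated patients vs. sham CPAP-treated patients", from baseline to 6 weeks. The second is the objective cough measure, namely the change in Leicester cough monitoring over those same 6 weeks on either therapy. The third covers five breath-condensate markers and reads: "Change in measurements of exhaled breath condensate 8 isoprostane, IL-6, nitrite/nitrate, H2O2 and LTB4 at baseline and at 6 weeks".

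Secondary end-points have their own heading directly below, so all three items belong to the primary tier by the document's own structure.

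The Statistical Analyses section describes the LCQ comparison and then adds: "Similar analyses are expected for GERD-QoL scores, Cough monitoring and EBC assessments". That sentence puts two primary items alongside GERD-QoL, which is a secondary end-point.

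The section on the number of subjects gives a "significant difference of 0.05 level", an 80% figure (read here as power), an SD, an expected effect and a sample size. All of these are for LCQ.

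Two further places bear on the role of each measurement. The Background describes the purpose as to "assess changes in subjective and objective cough measures in chronic cough patients with comorbid OSA". Purpose and Objectives includes breath condensate among the planned cough assessments but describes it as "Measures of airway inflammation using exhaled breath condensate". The aim stated there is that treating sleep apnoea makes cough better or ends it.

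**The concern.** When several end-points share the primary tier, the plan has to say what counts as success. Three readings fit this text: LCQ alone decides, any one result suffices, or all must be significant. The same data can give different conclusions under each, and nothing in the plan prevents the choice being made after the results are known.

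If any one result suffices, the trial's false-positive rate is well above 0.05. Five of the seven chances are inflammatory markers, which do not measure cough. If all must succeed, the error rate is controlled, but the trial was not sized for that. The document combines protocol and SAP and refers to no separate analysis plan where the rule might be found.

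**Working it through.** **The plan's own figures.** Inflating 19 per group for 33% attrition gives 19/(1 − 0.33) = 28.4, rounded up to 29, and 2 × 29 = 58, as stated. The 19 does not follow from the printed inputs alone. With SD 4.14, difference 2.58, two-sided 0.05 and 80% power, n = 2 × 4.14² × (1.96 + 0.8416)² / 2.58² = 40.4, so 41 per group. A baseline–follow-up correlation of about 0.76 to 0.78 in a change-score analysis would give 19, but no correlation is stated. That is a separate matter. What counts here is that the calculation concerns LCQ and nothing else.

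**Number of measurements.** LCQ 1 + cough monitoring 1 + condensate markers 5 (nitrite/nitrate counted as one) = 7. It is 8 if nitrite and nitrate are tested separately, and 3 if only the numbered items are counted.

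**Assumptions.** The documents give neither sidedness nor correlations, and do not state a between-arm test for items 2 and 3. I assume one between-arm test per measurement, each at two-sided 0.05, with no true effect on any, and show a range of correlations.

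**Family-wise error if any one result counts.** For k independent tests it is 1 − 0.95^k. For normal test statistics with common correlation r and c = 1.96, it is

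1 − ∫ [Φ((c − √r·w)/√(1−r)) − Φ((−c − √r·w)/√(1−r))]^k φ(w) dw.

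| Tests | r = 0 | r = 0.3 | r = 0.5 | r = 0.8 |
|---|---|---|---|---|
| 7 | 30.2% | 27.2% | 23.0% | 14.9% |
| 3 | 14.3% | 13.6% | 12.5% | 9.8% |

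Eight independent tests give 1 − 0.95^8 = 33.7%. The upper bound for seven tests under any dependence is 7 × 0.05 = 35%.

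**False success on a condensate marker alone**, with neither LCQ nor cough monitoring significant:

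- Independent: (1 − 0.95^5) × 0.95² = 20.4%, which is 0.2042/0.3017 = 68% of all false positives.
- Correlated, as the seven-test error minus the two-test error: 0.2296 − 0.0907 = 13.9% at r = 0.5, and 0.1486 − 0.0781, or 7.1% before rounding of the inputs, at r = 0.8.

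**Power if all must succeed**, assuming each test alone has 80% (the plan supports this for LCQ at most). For k independent tests it is 0.8^k. With correlation r it is ∫ [Φ((0.842 + √r·w)/√(1−r))]^k φ(w) dw.

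- All seven: 0.8^7 = 21% if independent, 45% at r = 0.5, 60% at r = 0.8.
- LCQ and cough monitoring only: 0.8² = 64% if independent, 73% at r = 0.8.

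**Cost of a plain Bonferroni correction over seven**, for comparison. Each test is at 0.05/7 = 0.00714. The SD implied by 19 per group is 2.58/[(1.96 + 0.8416) × √(2/19)] = 2.84. LCQ power at 19 per group then falls from 80% to about 54%. Restoring 80% takes 31 per group, or 31/0.67 = 46.3, rounded up to 47, after attrition: 94 in total against 58.

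**The case against.** The strongest reply is that LCQ is plainly the intended lead. It is listed first, it is the only primary item worded as a comparison of the two arms, it is the only variable named in the main analysis sentence, and it is the only basis for the sample size. On that reading nothing is inflated. The inference is reasonable, but it remains an inference. List order does not bind the analyst, the other six measurements carry the same label, and the Background does not rank the subjective above the objective cough measure.

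Second, seven is a count made from the text. The plan numbers three items, and between-arm tests at 0.05 for the other six measurements are inferred. This stands as a limit on the size. On the plan's own numbering the figures are 14.3% and 9.8%, still about two to three times 0.05.

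Third, the aim concerns cough, so a reader could reject a claim resting on a condensate marker alone. True, but that gives grounds for argument; it is not a pre-specified rule. Likewise, nothing in the text favours requiring all seven, and 80% power per marker has no source; that case only shows where the reading would lead.

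Fourth, LCQ and cough monitoring as co-primaries may be as faithful to the Background as LCQ alone. That is a fair alternative, and it is taken up under the fix. None of these points closes the gap itself.

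**Conclusion.** The concern holds and must be fixed before analysis. The plan puts LCQ, cough monitoring and five condensate markers in the primary tier and gives no lead, order, success rule or adjustment.

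If any one result counts, the false-positive rate for the trial lies between about 10% (three tests, correlation 0.8) and 30% (seven independent tests) under the assumptions above. Between 7% and 20% of null trials would be positive on an inflammatory marker only. Inflation arises only under the any-one rule, but the plan does not exclude that rule.

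Confidence in the gap is high. Its exact size depends on the number of tests and on correlations that the documents do not give.

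**What to change.** In the end-point and statistics sections:

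- Name the week-6 CPAP-versus-sham difference in LCQ change as the single primary end-point. It is the only variable with a sample-size calculation.
- Test 24-hour cough monitoring second, at 0.05 and only if LCQ is significant. Name in advance the one cough-monitor metric to be tested, which the documents do not do.
- Label the five condensate markers exploratory or mechanistic, with nominal p-values.

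This holds family-wise error at 0.05 for the two cough measures. It costs a text change only: data collection is unchanged, and the fix adds nothing to the 19 and 29 per group, though it does not show that those numbers are adequate. The downside is that an isolated cough-monitor or condensate result could no longer be claimed as a primary success.

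If the sponsor prefers LCQ and cough monitoring as co-primaries that must both succeed, error is also controlled. The price is joint power of 64% to 73% if each alone has 80%, and cough monitoring would need a sample-size calculation of its own.

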### SECONDARY END-POINTS

- Change in GERD-QoL scores, change in LDQ scores at 6 weeks
- Change in LCM at 12 weeks compared to 6 weeks in sham CPAP patients
- CPAP compliance at 6 weeks and 12 weeks.

## STUDY PROTOCOL

Subjects with randomized to straight CPAP (either at 10cm or at a pressure determined during PSG) OR sham CPAP (1-2cm) following mask-fitting session during PSG or prior to that. After 6 weeks of therapy, patients will evaluated for above-mentioned end-points and study analyses will be done. Patients will be then placed on CPAP (as prescribed by PSG) and followed at 12 weeks again.

**VISIT 1                    SCREENING AND ADMINISTRATION OF QUESTIONNAIRES (LCQ, GERD-QoL, SNOT-20, LDQ, ALQ; MEASUREMENT OF EBC AND COUGH MONITORING FOR 24 HOURS)**

PATIENTS WILL BE ON STRAIGHT CPAP FOR 6 WEEKS OR ON SHAM CPAP FOR 6 WEEKS.

VISIT 2 (+6wk) ADMINISTRATION OF LCQ, GERD-QoL, LDQ, SNOT-20, ALQ, SMART-CARD DATA DOWNLOAD, EBC, COUGH MONITORING FOR 24 HOURS

## PATIENTS ON STRAIGHT CPAP FOR 6 WEEKS

## VISIT 3 (+12 wk) ADMINISTRATION OF LCQ, SMART-CARD DATA DOWNLOAD, EBC

## STATISTICAL ANALYSES

Each patient will serve as his or her control in terms of 6 weeks assessment of LCQ change following sham CPAP or straight CPAP therapy. Similar analyses are expected for GERD-QoL scores, Cough monitoring and EBC assessments.

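### The analysis text describes each patient as own control and never states a CPAP-versus-sham comparison: incomplete for LCQ, unstated in the end-point and analysis text for cough monitoring, and unstated anywhere for the EBC markers

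*Combined protocol and SAP*

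**What the plan says.** Under the heading "Statistical Methods, Data Analysis and Interpretation", the Statistical Analyses section consists of two sentences. The first is "Each patient will serve as his or her control in terms of 6 weeks assessment of LCQ change following sham CPAP or straight CPAP therapy". The second is "Similar analyses are expected for GERD-QoL scores, Cough monitoring and EBC assessments". No test, model, treatment contrast or estimate is named.

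The other relevant places are:

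- **Primary End-Point, item 1 (LCQ).** It states the contrast: "Change in LCQ score in CPAP-treated patients vs. sham CPAP-treated patients".
- **Primary End-Point, item 2 (cough monitoring).** "Change in Leicester cough monitoring measured at baseline and at 6 weeks after CPAP or sham-CPAP therapy". Both therapies are named but not compared.
- **Primary End-Point, item 3 (five EBC markers).** "Change in measurements of exhaled breath condensate 8 isoprostane, IL-6, nitrite/nitrate, H2O2 and LTB4 at baseline and at 6 weeks". No arm is mentioned.
- **Secondary End-Points.** "Change in GERD-QoL scores, change in LDQ scores at 6 weeks", again without a contrast. LDQ does not appear in the Statistical Analyses section at all.
- **Study Protocol.** After six weeks, "patients will evaluated for above-mentioned end-points and study analyses will be done". This only points back to the end-point list.
- **Number of Subjects to be Enrolled.** The trial is sized on an LCQ difference between two groups, and a repeated-measures mixed model is named for that calculation.
- **Background and Introduction.** The study is described as using CPAP and sham arms to assess subjective and objective cough. That sentence does not mention EBC.

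**The concern.** The Background presents a placebo arm as what earlier work on CPAP and cough lacked. A sham arm removes placebo response, regression to the mean and time trends only if the two arms are compared. A change from a patient's own baseline contains all three. If an analyst took the own-control sentence at face value and tested change within each arm, those effects would be credited to CPAP. The plan itself expects LCQ to rise on placebo, so this bias is foreseeable from its own figures.

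The gap also leaves the planned analysis open. A within-arm result and a between-arm result could each be reported as the one the plan called for.

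**Working it through.** **1. Which end-points have a stated contrast**

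| Six-week variable | End-point text | Statistical Analyses | Elsewhere |
|---|---|---|---|
| LCQ | CPAP vs sham | own control | two-group sizing |
| Cough monitoring | both therapies named, not compared | similar analyses | intent in Background |
| EBC (5 markers, nitrite/nitrate counted as one) | no arm named | similar analyses | listed as an assessment in Purpose and Objectives, no contrast |
| GERD-QoL | no arm named | similar analyses | none |
| LDQ | no arm named | not mentioned | none |

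**2. The plan's own LCQ figures** (Number of Subjects to be Enrolled)

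- CPAP gain 4.1, placebo gain 1.1. The expected difference reproduces: 4.1 − 1.1 = 3.0.
- Share of the before/after CPAP gain that is placebo gain: 1.1/4.1 = 27%.
- Overstatement if the before/after gain is read as the effect: 4.1/3.0 − 1 = 37%.
- Attrition reproduces: 19/(1 − 0.33) = 28.4, rounded up to 29 per group.
- The 19 per group cannot be confirmed or refuted, because the within-patient correlation is not given. The point does not depend on it.

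**3. False-positive rate for LCQ if inference is within-arm**

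Assumptions: no true CPAP effect, so both arms gain 1.1 points; two-sided 5% tests; score SD 4.14 at both times (from the plan); baseline-to-week-6 correlation ρ from 0 to 0.78 (not in the documents). The upper value is the correlation at which a two-sample t-test on change has 80% power for 2.58 points with 19 per arm. That requires a change SD of 2.76, and 1 − (2.76/4.14)²/2 = 0.78.

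SD of change = 4.14 × √(2(1 − ρ)). Let p be the noncentral-t probability that one arm's mean change is significant in the direction of improvement. The arms are independent, so the rule *CPAP significant, sham not* favours CPAP with probability p(1 − p).

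| ρ | SD of change | p, n = 19 | p(1 − p) | p, n = 29 | p(1 − p) |
|---|---|---|---|---|---|
| 0 | 5.85 | 0.118 | 0.104 | 0.163 | 0.136 |
| 0.25 | 5.07 | 0.144 | 0.123 | 0.203 | 0.162 |
| 0.50 | 4.14 | 0.194 | 0.156 | 0.282 | 0.202 |
| 0.78 | 2.76 | 0.376 | 0.235 | 0.544 | 0.248 |

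The rule that looks at both arms therefore gives 10–23% at 19 per arm and 14–25% at 29. It cannot exceed 25%, because p(1 − p) peaks at p = 0.5. Testing the CPAP arm alone gives p itself: 12–38% and 16–54%. A two-sided 5% between-arm test favours CPAP in 2.5% of trials at any ρ, since the common gain cancels. The 29-per-arm figures assume that none of the planned attrition occurs.

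**4. Cough monitoring and EBC**

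The documents give no placebo change for these measures. For an assumed common drift toward improvement of 0.1 to 0.4 change-SDs, p runs from 0.061 to 0.379 at 19 per arm and from 0.075 to 0.548 at 29. The rule that looks at both arms then gives 6–24% and 7–25% per variable, against 2.5% between arms. With no drift, p is 2.5%.

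**The case against.** The strongest reply is that own control simply means change from each patient's own baseline. The sentence names both therapies, so the changes could then be compared between arms, in agreement with the first primary end-point and the two-group sizing. That stands: for LCQ the text is incomplete, and it does not contradict the rest of the plan. On the same view, similar analyses could carry the between-arm comparison over to the other measures. That is plausible, but the sentence being carried over does not contain the comparison, and the mixed model is named only for sizing the LCQ comparison.

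A reader might infer that no comparison with sham is intended. The documents do not support this: no section says inference is within-arm, and the randomised, double-blind sham design implies the contrast.

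A reader might also count cough monitoring and the five EBC markers together and conclude that six of seven primary variables have no contrast anywhere. That holds only for the end-point and analysis text. The Background covers objective cough, so only the EBC markers, which form a single end-point item, have no stated contrast in any section.

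Finally, the rates of 38% and 54% apply only if the sham result is ignored. The own-control sentence covers both arms, so the rule that uses both is the fairer illustration.

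**Conclusion.** The point holds as a gap in specification that should be fixed, strongest for EBC, weaker for cough monitoring, and a matter of alignment for LCQ. It rests on the wording of the sections cited. The 27% follows from the plan's own figures. The false-positive rates are conditional on three things: a literal within-arm reading, no true CPAP effect, and correlations or drifts that the documents do not give. They show what the wording would permit; they do not predict what the investigators will do.

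**What to change.** Replace the first sentence of Statistical Analyses, and the sentence on similar analyses, with:

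> *The primary analysis compares week-6 LCQ between the randomised CPAP and sham arms, adjusted for baseline LCQ (ANCOVA), and reports the difference with its 95% CI. Cough monitoring, each EBC marker, GERD-QoL and LDQ are compared between arms in the same way. Within-arm changes are descriptive only.*

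Add *CPAP vs. sham CPAP* to primary end-points 2 and 3.

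The between-arm contrast is the necessary repair. A between-arm test of change scores would also be valid; baseline adjustment is a precision gain that needs no extra data. The cost is wording only: baseline and week-6 values are already collected in both arms, so no patients, visits or measurements are added.

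### Cough-monitor counts and breath-condensate markers are primary, yet the only analysis given is change like the LCQ; specify log-scale analysis adjusted for log baseline, with rules for zeros and values below detection

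*Combined protocol and SAP*

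**What the plan says.** The section PRIMARY END-POINT has three items. The first is LCQ change, CPAP against sham. The second is "Change in Leicester cough monitoring measured at baseline and at 6 weeks after CPAP or sham-CPAP therapy". The third is "Change in measurements of exhaled breath condensate 8 isoprostane, IL-6, nitrite/nitrate, H2O2 and LTB4 at baseline and at 6 weeks".

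The section STATISTICAL ANALYSES gives one rule, written for the LCQ: "Each patient will serve as his or her control in terms of 6 weeks assessment of LCQ change". It then extends that rule: "Similar analyses are expected for GERD-QoL scores, Cough monitoring and EBC assessments".

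The only model named is in NUMBER OF SUBJECTS TO BE ENROLLED, where the LCQ sample size is derived "assuming no attrition using a mixed models analysis of repeated measures data". Its terms are not listed.

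For cough monitoring and EBC the documents give no scale, transformation, baseline covariate, summary measure from the 24-hour recording, or rule for zeros or values below a detection limit.

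**The concern.** The LCQ is a questionnaire score. A 24-hour cough count and a marker concentration are different kinds of variable: neither can fall below zero, and the spread of such measures commonly grows with their level. If CPAP removes a given share of coughs, the fall is large in a patient who coughs a lot and small in one who coughs little. Differences between patients in untransformed change then mostly reflect who started high, and the treatment contrast is estimated with that noise in it. For EBC the parallel is a few high concentrations.

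Two of the three primary items are of this type, and the sample size was set for the LCQ alone. What is at stake is the chance of detecting a real effect on the objective cough measure and the markers, and the stability of the estimate. The baseline values needed for a better analysis are already collected at Visit 1.

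**Working it through.** **1. The plan's own figure.** It concerns the LCQ only: "To achieve 80% difference to detect a significant difference of 0.05 level for a difference means of 2.58, 19 subjects per group needed", with "mean change in LCQ with CPAP was + 4.1 (with 4.14 SD in baseline and followup LCQ scores".

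- Attrition: 19 / (1 − 0.33) = 28.4, so 29 per group. This reproduces.
- The 19, by the two-sample formula (two-sided 0.05, 80% power): n = 2 × (1.96 + 0.84)² × 4.14² / 2.58² = 40.4, so 41 per group. The printed inputs alone do not give 19.
- To give 19, the analysis SD must be about 2.84. That means an unstated baseline/follow-up correlation of about 0.76 for a change score (1 − 2.84² / (2 × 4.14²)) or about 0.73 for ANCOVA (√(1 − 2.84² / 4.14²)).

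This does not show the 19 to be wrong, and the present point does not depend on it. No figure is given for cough counts or EBC, so there is none to reproduce.

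**2. Inputs for the comparison.** From the documents: 19 per arm after attrition, 29 enrolled, and alpha 0.05 (sidedness not stated; two-sided taken). Assumed, because the documents give nothing: log-normal values at baseline and week 6, no change on sham, CPAP/sham ratio 0.5, correlation 0.6 on the log scale, and log-SD from 0.3 to 1.0.

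**3. Four analyses compared by simulation.** Raw change: t-test on week 6 minus baseline. Raw ANCOVA: week 6 adjusted for baseline. Log change: t-test on the log ratio. Log ANCOVA: log week 6 adjusted for log baseline.

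| Per arm | Log-SD | Raw change | Raw ANCOVA | Log change | Log ANCOVA |
|---|---|---|---|---|---|
| 19 | 1.0 | 30% | 49% | 63% | 72% |
| 19 | 0.6 | 76% | 97% | 97% | 99% |
| 19 | 0.3 | 100% | 100% | 100% | 100% |
| 29 | 1.0 | 42% | 68% | 83% | 89% |

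Simulation error is one to two points; a repeat run agreed within that.

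**4. Closed-form check of the log columns (19 per arm, log-SD 1.0).** The effect is ln 2 = 0.693.

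- Log change: SD = √(2 × (1 − 0.6)) = 0.894; SE = 0.894 × √(2/19) = 0.290; 0.693 / 0.290 = 2.39. On 36 df, power is about 64%.
- Log ANCOVA: SD = √(1 − 0.6²) = 0.80; SE = 0.80 × √(2/19) = 0.260; 0.693 / 0.260 = 2.67. On 35 df, power is about 74%, slightly optimistic because chance baseline imbalance is ignored.

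**5. Splitting the gain (19 per arm).** At log-SD 1.0 the gain from raw change to log ANCOVA is 72 − 30 = 42 points, of which baseline adjustment alone gives 49 − 30 = 19, or 45%. At log-SD 0.6 the gain is 99 − 76 = 23 points, of which baseline adjustment gives 97 − 76 = 21, or 91%.

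**6. A smaller effect.** At ratio 0.6, correlation 0.5, log-SD 0.8 and 19 per arm, power is 27%, 45%, 48% and 59% in the same order. Over log-SD 0.3 to 1.2, correlation 0.5 or 0.7 and ratio 0.5 to 0.7, log ANCOVA was never below raw change.

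**7. Influence of high values.** At log-SD 0.8 to 1.2 with a working treatment, the 10% of patients with the highest baseline (4 of 38) supply about 45% to 65% of the variance of raw change. At log-SD 0.3 they supply about 25%.

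**8. No treatment effect.** Raw change rejects in 3.6% to 5.0% of trials at the nominal 5%.

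**The case against.** The strongest reply is that the plan does not prescribe the weak analysis. A reader might infer that it fixes raw change as the method. It does not: the text says change, and a loosely worded similarity to the LCQ analysis could cover log change or a ratio to baseline. This stands. Untransformed change is the natural reading, not a stated rule. But if another scale was intended it is nowhere recorded, and choosing the scale of a primary end-point after seeing the data would be worse.

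Second, the mixed model named for the LCQ sample size might carry over. If it modelled baseline suitably it would recover part of the loss without any log, as the raw ANCOVA column shows. This also stands, so the gap between raw change and log ANCOVA must not be credited to the log scale alone. But the model's terms are not given, and it would not by itself change the scale.

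Third, log-normal data with a constant proportional effect make the log analysis correct by construction. Fair: the size is conditional on this. In one departure, where CPAP acted only in patients above the median baseline (log-SD 0.6, correlation 0.6, ratio 0.4, 29 per arm), raw ANCOVA reached 85% and log ANCOVA 88%, so the log added little beyond baseline adjustment.

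Fourth, the simulation had no zeros or detection limit. For EBC the direction is argued rather than tested, and a log analysis can depend on how values near zero are treated.

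A reader might also infer that a few heavy coughers could create a false positive. The results under no effect do not support that.

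**Conclusion.** The point holds as a gap in specification with a clearly better option available. For two of the three primary items the only stated method, read naturally, is untransformed change without baseline adjustment. Under right skew and a proportional effect this costs power and makes the estimate depend heavily on the patients with the highest values. The type I error rate is not inflated.

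The size is conditional. At 19 per arm, a halving and correlation 0.6, the gain from raw change to log ANCOVA is 42 points at log-SD 1.0, 23 points at 0.6 and nil at 0.3. Between about half and nearly all of that gain comes from baseline adjustment alone. The 19 per arm is the number left after the plan's 33% attrition; the 29-per-arm figures apply only if every enrolled patient is measured at week 6.

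The documents support neither a claim that the trial will miss a halving of cough nor a single figure for the power lost, since they give no distribution, correlation or expected effect for these measures. The EBC part is the less certain half. This should be changed, but it does not invalidate the design.

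**What to change.** In STATISTICAL ANALYSES, replace the sentence on similar analyses, as far as it covers cough monitoring and EBC, with a rule of this kind:

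- For the 24-hour cough count and for each EBC marker, compare CPAP with sham at week 6 on the log scale, with log baseline as covariate.
- Report the CPAP/sham ratio of geometric means with its 95% CI.
- Fix in advance how zero counts and values below the detection limit are handled, and for EBC add a sensitivity analysis to that rule.
- Keep untransformed change from baseline as a descriptive summary.

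The cost is analysis wording only: no added patients, visits or measurements. The downsides are that effects read as ratios rather than differences, and that EBC results may be sensitive to the below-detection rule, which is why that rule has to be set before the data are seen.
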